2.2 Scientific Rationale

Question: Is the RRT a sensitive or specific screening tool for detecting anterior or posterior segment pathology under physiologic conditions or following pupillary dilation in the pediatric population?

Hypothesis: The RRT is not a sensitive or specific screening tool for detecting anterior or posterior segment pathology in the pediatric population even following pharmacologic pupillary dilation.

Visual acuity and disease are difficult to assess in the pediatric population and especially younger children due to normal developmental changes as well as

challenges in patient cooperation or symptom reporting. However, assessing visual and anatomic abnormalities in this age group remains of paramount importance to avoid visual morbidity, and rarely systemic complications, from undetected ophthalmic pathology. The RRT is currently recommended by the Joint Committee as an initial screening test for anterior and posterior segment ocular abnormalities in the pediatric population. The recommendations suggest that dim room lighting aids in the accuracy of the RRT. However, limited available evidence to date has demonstrated that the RRT is not a sensitive or specific test for detecting posterior segment pathology. Furthermore, there are no studies to date specifically examining the effect of dim lighting conditions or pupillary dilation on the sensitivity and specificity of the RRT.

This study aims to evaluate the sensitivity and specificity of the RRT for detecting anterior or posterior segment pathology in both ambient and dark lighting conditions, before and after pharmacologic dilation.

2.3 Potential Risks

There is minimal immediate or long-term risk in this study. The interventions used are included in a standard ophthalmologic exam. Patient's may experience mild discomfort from the light of the equipment (direct ophthalmoscope) shone into their eyes. Additionally, patients have a risk in breach of confidentiality from usage of PHI data. However, all steps in accordance with CNHS policy will be performed in order to ensure patient confidentiality. These minimal risks are worth the potential benefit of understanding how to perform ophthalmologic screening in the pediatric medical home.

2.4 Potential Benefits

Study benefits to subjects include, but are not limited to, careful evaluation of known anterior or posterior segment ophthalmologic disease.

Study benefits to the greater community include, but are not limited to, helping improve vision screening guidelines for the early detection and treatment of eye disease.

Section 3: Objectives and Endpoints

3.1 Primary Objective(s)

The primary outcomes of this study will be the sensitivity and specificity of the RRT in detecting anterior segment pathology, as well as the sensitivity and specificity of the RRT in detecting posterior segment pathology.

3.2 Secondary Objective(s)

The secondary outcomes of this study will be the sensitivity and specificity of the RRT in detecting anterior segment or posterior segmented pathology following pharmacologic dilation.

3.3 Primary Outcome Measure(s)

Number of eyes with posterior segment pathology correctly identified as having posterior segment pathology and incorrectly identified as not having pathology. Number of healthy eyes correctly identified as being healthy.

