2.1 Background Information and Relevant Literature

The early detection of ophthalmic pathology is critical for the prevention of vision loss and systemic morbidity in rare cases. The American Academy of Pediatrics (AAP), the American Association for Pediatric Ophthalmology and Strabismus (AAPOS), the American Academy of Ophthalmology (AAO), and the American Association of Certified Orthoptists (AACO) continue to advocate for inclusion of the red reflex test (RRT) as part of the ophthalmologic screening exam in the general pediatrics clinic. However, studies to date have demonstrated that there are potential limitations to the RRT, especially in its ability to accurately and reliably detect posterior segment pathology.

Standard procedure for the RRT currently involves viewing both eyes at arms length in lighted room followed by a darkened room to assess for symmetry of the reflection in terms of brightness and color. If an abnormality is suspected, then the operator may move closer for further inspection. With its current application, the RRT introduces subjectivity in interpretation and likely variation in pupillary reflection based on factors such as, the specific lighting condition, degree of physiologic dilation, and patient movement. Differences in operator experience with the RRT may further compound the shortcomings of this exam technique. These factors unfortunately reduce the accuracy and reliability of the RRT as a screening measure.

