3.4 Secondary Outcome Measure(s)

Number of eyes with anterior segment pathology correctly identified as having anterior segment pathology and incorrectly identified as not having pathology. Number of healthy eyes correctly identified as being healthy.

Section 4: Study Design

Prospective study

Section 5: Study Enrollment and Withdrawal

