5.1 Study Population, Recruitment and Retention

Pediatric patients will be recruited through clinical practice at the designated study sites. Participants with known anterior segment or posterior segment pathology will be eligible for inclusion. Patients who have a history of disease, treatments and/or surgical procedures affecting the ability for normal pupillary reaction are excluded. An equal number of age matched participants with a normal anterior and posterior segment exam will be recruited from routine outpatient clinic visits. Informed consent will be obtained and will include an option to be considered for medical photography. Participants may opt out of photography and still be included in the study. For Spanish speaking participants, a telephone interpreter will be used for study recruitment and informed consent. A Spanish informed consent (developed by a Spanish medical translator from our English written consent) will be provided. Current estimated number of subjects required for the study is 200 total including 100 controls. Patient charts will be accessed from date of birth to patient's current age using either Cerner or Epic depending on the study site location. Examiners will include ophthalmology residents with one completed year of ophthalmology training. They will be blinded to participants' ophthalmologic history.

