8.3 Analysis Datasets

The baseline demographic data will be presented descriptively. Continuous data will be summarized as mean with standard deviation or median with interquartile range depending on the distribution of the data. Categorical data will be summarized using frequencies with percentage. Summary demographic statistics between patients with and without eye abnormalities will be compared using unpaired t-test (normal) and/or Mann-Whitney U test (skewed) for continuous data, and Chi-square test and/or Fisher's exact test (if any of the expected cell frequencies are <5) for categorical data. Normality assumption will be checked by using statistical test (e.g., Shapiro Wilk test) as well as graphical methods (e.g., histogram, q-q plot).

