8.4 Description of Statistical Methods

To assess our primary and secondary hypothesis, sensitivity and specificity of the red reflex test (RRT) will be determined along with their 95% confidence interval using contingency tables for both anterior and posterior segment pathology. Positive predictive value (PPV), negative predictive value (NPV), and area under ROC curve (AUC) will also be determined. We will also compare sensitivity and specificity of RRT for both anterior and posterior pathology between with and without pharmacologic dilation using two-sided McNemar's test for correlated proportions.

All statistical tests will be two-sided and will be performed at the 5% level of significance unless otherwise stated. Stata 15.1 software will be used for all statistical analyses.

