8.5 Sample Size

*Our sample size calculation is based on our primary hypothesis. Assuming a 75% prevalence of anterior or posterior segment pathology and a sensitivity of 90% in our sample, a total of **59** patients will be required to construct a two-sided 95% sensitivity confidence interval with a width of at most +/-10%. Under the same assumptions, the sample size needed for a two-sided 95% specificity confidence interval of +/-10% around 80% is **280**. We will take the larger one of these two, which is **280**. The power analysis was carried out using PASS 2019 software.*

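### Outcomes are counted in eyes, but the analysis names no unit and makes no allowance for two eyes per child, so eye-level intervals would be too narrow and the McNemar test can reject too often

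*Combined protocol and SAP*

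**What the plan says.** - **Outcomes, in eyes.** Section 3.3 counts the "Number of eyes with posterior segment pathology correctly identified as having posterior segment pathology and incorrectly identified as not having pathology", and section 3.4 the "Number of eyes with anterior segment pathology correctly identified as having anterior segment pathology". Both also count healthy eyes correctly called healthy.
- **Analysis, no unit.** Under section 8.4, "sensitivity and specificity of the red reflex test (RRT) will be determined along with their 95% confidence interval using contingency tables". For the secondary aim: "We will also compare sensitivity and specificity of RRT for both anterior and posterior pathology between with and without pharmacologic dilation", by a two-sided McNemar test. The Protocol Summary repeats this text. Neither place says whether a table entry is an eye or a child.
- **Patients elsewhere.** Section 8.3: "Summary demographic statistics between patients with and without eye abnormalities will be compared". Section 8.5 states how many "patients will be required to construct a two-sided 95% sensitivity confidence interval with a width of at most +/-10" percent.
- **Numbers of children.** Section 5.1: "Current estimated number of subjects required for the study is 200 total including 100 controls".
- **The test itself.** Section 2.1 describes the standard procedure as "viewing both eyes at arms length in lighted room followed by a darkened room to assess for symmetry of the reflection".

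No section gives a within-child correlation, a clustered interval or test, a rule for choosing one eye, or a rule for turning two eyes into one result.

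**The concern.** The estimates with their intervals are the primary results (section 3.1), and the dilation comparison serves the secondary aim. Both depend on what one row of the data is, and the plan leaves that open. Neither reading works as written.

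- **If the tables hold eyes**, as 3.3 and 3.4 require, the methods in 8.4 treat a child's two eyes as independent. Section 2.1 gives reason to expect positive correlation. The eyes are viewed together and compared, and the factors it lists as affecting the reading (lighting, physiologic dilation, movement, operator experience) are largely common to both. McNemar's test handles the pairing of readings before and after dilation; it does not handle the pairing of eyes.
- **If the tables hold children**, 8.4 does not produce the outcomes in 3.3 and 3.4. A child with one diseased and one normal eye then has no defined result.

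The plan also does not say whether the unaffected fellow eye of a unilateral case counts as a healthy eye. Because the test judges symmetry, such an eye may read differently from a control child's eye. That could move the specificity estimate itself as well as its interval.

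**Working it through.** **1. Reproduce section 8.5.** Inputs: sensitivity 90%, specificity 80%, prevalence 75%, ±10 points (total width 0.20). Taking exact (Clopper-Pearson) intervals and one independent result per patient:

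- At 90%, the width is 0.201 at n = 43 and 0.198 at n = 44; 44 / 0.75 = 58.7, so **59**.
- At 80%, the width is 0.200 (just above the limit) at n = 69 and 0.199 at n = 70; 70 / 0.25 = **280**.

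Both figures match. Wald intervals would give 47 and 248, and Wilson intervals 50 and 240. So 8.5 is a patient-level calculation, while 3.3 and 3.4 are at eye level.

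**2. Specificity, eye-level reading.** Take the 100 controls of section 5.1, both eyes each (200 eyes), and 80%. Let ρ be the correlation between a child's two readings. It is not in the documents, so a range is shown. The design effect is DE = 1 + ρ.

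- Naive half-width: 1.96 × √(0.8 × 0.2 / 200) = 5.5 points.
- Correct half-width: 5.5 × √DE. True coverage of the naive interval: 2Φ(1.96/√DE) − 1.

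| ρ | Correct half-width (points) | Coverage, formula | Coverage, simulated Clopper-Pearson |
|---|---|---|---|
| 0.3 | 6.3 | 91.4% | 92.7% |
| 0.5 | 6.8 | 89.0% | 89.9% |
| 1.0 | 7.8 | 83.4% | 83.0% |

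**3. Sensitivity, eye-level reading.** Let b be the share of cases with disease in both eyes (also not given). Then m cases give m(1 + b) eyes. The variance of the number detected is p(1 − p) × m(1 + b + 2bρ), so DE = 1 + 2bρ/(1 + b). At ρ = 0.5:

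| b | DE | Coverage |
|---|---|---|
| 0 | 1.00 | 95.0% |
| 0.3 | 1.23 | 92.3% |
| 0.5 | 1.33 | 91.0% |
| 1 | 1.50 | 89.0% |

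Example, assuming 50 cases in one segment, b = 0.5 and sensitivity 90%: 75 eyes, naive 1.96 × √(0.09 / 75) = 6.8 points, correct 6.8 × √1.333 = 7.8 points.

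**4. McNemar's test.** Simulated with no true dilation effect, 20,000 runs per setting. Assumptions: 20% of eyes change reading with dilation, and ρ is now the correlation between a child's two eyes of that change. The table gives rejection rates at nominal 5%. Section 8.4 does not say whether the asymptotic or the exact version is meant.

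| Setting | Version | ρ = 0.3 | ρ = 0.5 | ρ = 1 |
|---|---|---|---|---|
| 100 children, all giving two eyes | asymptotic | 8.3% | 10.7% | 17.4% |
| | exact | 6.2% | 8.4% | 13.5% |
| 100 children, half giving two eyes | asymptotic | 7.6% | 9.1% | 13.4% |
| | exact | 4.9% | 6.1% | 9.6% |

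With ρ = 0 and two eyes each, the rates are 5.1% and 3.5%. A separate simulation assuming 30% of eyes change, with 100 two-eyed children, gave asymptotic rates of 8.0%, 11.0% and 13.8% at ρ = 0.25, 0.5 and 0.75. A cluster-adjusted McNemar test on the same data gave 5.0%, 5.1% and 5.0%.

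**The case against.** The strongest reply is that the plan may intend one result per child. Sections 8.3 and 8.5 speak of patients, the sample size reproduces on that basis, and a single comparison for symmetry fits a per-child reading. There would then be no distortion of intervals or tests. This is a fair reading, but it contradicts the eye counts in 3.3 and 3.4, and the plan has no rule for combining two eyes. The fault changes form; it does not disappear.

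Second, the sizes rest on assumed values of ρ, b and the share of eyes that change. That stands, and they are illustrations only.

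Third, the McNemar figures for 100 two-eyed children suit the controls, hence specificity. For sensitivity, 50 cases with b = 0.5 and 20% of eyes changing give exact-test rates of 4.4%, 5.4% and 9.0% at ρ = 0.3, 0.5 and 1. With 10% changing, they are 2.8%, 3.7% and 6.7%. So the exact test is often at or below 5% there. The asymptotic test stays inflated, at about 6% to 13%. The excess is therefore possible, not certain.

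Fourth, the half-widths move by only about one point at ρ of 0.3 to 0.5, and no acceptance threshold is set. A contrast as large as the one cited in section 2.1 (99.6% against 4.1%) would not be overturned. That is true, and it limits the seriousness. The dilation comparison is a test at 5%, however, and has no such margin.

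Fifth, no data form is shown, so recording by eye is implied by 3.3 and 3.4 but not confirmed.

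**Conclusion.** The concern holds. The unit of analysis is unresolved, and following 3.3 and 3.4 with the methods of 8.4 gives intervals that are too narrow whenever a child's two eyes are positively correlated. At a correlation of 0.5, nominal 95% coverage falls to about 89% for specificity in two-eyed controls. For sensitivity it is between 95% (all cases unilateral) and 89% (all bilateral). The dilation test can exceed its 5% level, most clearly in its asymptotic version and among controls.

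This rests on the eye-level reading and on positive correlation; with zero correlation there is no loss. The sample size is not harmed, because the corrected half-widths above stay within ±10 points. It should be fixed before analysis, so that the unit is not chosen after the data are seen.

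**What to change.** In section 8.4, name the unit of analysis and take one of two routes.

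1. **Keep the eye**, as in 3.3 and 3.4. Compute 95% intervals clustered on the child (GEE, cluster-robust variance or a bootstrap that resamples children), and compare readings before and after dilation with a clustered McNemar test or GEE.
2. **Use the child.** Define how two eyes combine into one result, for both the reference diagnosis and the test reading, and reword 3.3 and 3.4 to match.

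On the eye-level route, state whether healthy eyes include unaffected fellow eyes of unilateral cases, and report those eyes separately from control children's eyes.

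The cost is some wording and a few lines of code, with no change to the sample size. Data collection is unchanged provided readings are recorded by eye, as 3.3 and 3.4 imply; this should be confirmed. The price is somewhat wider intervals.

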3.4 Secondary Outcome Measure(s)

Number of eyes with anterior segment pathology correctly identified as having anterior segment pathology and incorrectly identified as not having pathology. Number of healthy eyes correctly identified as being healthy.

Section 4: Study Design

Prospective study

Section 5: Study Enrollment and Withdrawal

5.1 Study Population, Recruitment and Retention

Pediatric patients will be recruited through clinical practice at the designated study sites. Participants with known anterior segment or posterior segment pathology will be eligible for inclusion. Patients who have a history of disease, treatments and/or surgical procedures affecting the ability for normal pupillary reaction are excluded. An equal number of age matched participants with a normal anterior and posterior segment exam will be recruited from routine outpatient clinic visits. Informed consent will be obtained and will include an option to be considered for medical photography. Participants may opt out of photography and still be included in the study. For Spanish speaking participants, a telephone interpreter will be used for study recruitment and informed consent. A Spanish informed consent (developed by a Spanish medical translator from our English written consent) will be provided. Current estimated number of subjects required for the study is 200 total including 100 controls. Patient charts will be accessed from date of birth to patient's current age using either Cerner or Epic depending on the study site location. Examiners will include ophthalmology residents with one completed year of ophthalmology training. They will be blinded to participants' ophthalmologic history.

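### Section 8.5 sizes one pooled sensitivity, so its ±10-point precision is not secured for the primary posterior-segment estimate

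*Combined protocol and SAP*

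**What the plan says.** **Outcomes.** Section 3.1 names sensitivity and specificity for anterior pathology and, separately, for posterior pathology as primary. Section 3.3 gives the primary measure as "Number of eyes with posterior segment pathology correctly identified as having posterior segment pathology and incorrectly identified as not having pathology". Section 3.4 places the anterior counts under secondary measures, which differs from 3.1, but posterior sensitivity is primary on either reading. Section 3 defines no combined outcome.

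**Sample size.** Section 8.5, repeated in the Protocol Summary, starts from one pooled figure: "Assuming a 75% prevalence of anterior or posterior segment pathology and a sensitivity of 90% in our sample". It asks for a "two-sided 95% sensitivity confidence interval with a width of at most +/-10" (percentage points) and obtains 59 patients. For specificity it reports that the number for a "two-sided 95% specificity confidence interval of +/-10% around 80% is 280".

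**Enrolment.** Section 5.1 states "Current estimated number of subjects required for the study is 200 total including 100 controls" and "An equal number of age matched participants with a normal anterior and posterior segment exam will be recruited", so about 100 cases. On eligibility it says "Participants with known anterior segment or posterior segment pathology will be eligible for inclusion". The Protocol Summary (Study Population) says that patients with pathology will be divided into an anterior and a posterior group so that the two can be assessed separately. It gives no group sizes, and neither do 5.1, 5.2 or 5.5. The Protocol Summary also gives a participant range of 100 to 200.

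**The concern.** The quantity that was sized is not a quantity the study will report as an outcome. A pooled sensitivity at ±10 points says nothing about the width of the posterior interval, which depends only on how many posterior cases are enrolled and on the sensitivity in that group. The plan fixes no such number.

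The gap falls on the question that motivates the study. Section 2.1 describes the anterior evidence as plentiful and the posterior evidence as lacking, and the hypothesis in 8.2 is about posterior detection only. Enrolment could reach its total and still leave a posterior interval wider than the plan claims. That cannot be repaired once enrolment has closed.

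**Working it through.** **Inputs.** From 8.5: two-sided 95% interval, half-width 10 points (full width 20), pathology prevalence 75%, sensitivity 90%, specificity 80%. From 5.1: 200 subjects including 100 controls. From 2.1: posterior sensitivity of 4.1% and 0% in the two cited newborn studies. The posterior share of cases is not in the documents, so the group sizes of 20 to 50 below are assumptions.

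**Step 1: reproduce the plan's figures.** Use the exact (Clopper-Pearson) interval for x = n × p positives out of n:

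- lower limit = Beta(0.025; x, n − x + 1)
- upper limit = Beta(0.975; x + 1, n − x)

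Take the smallest n with full width at most 20 points, then divide by the proportion of the sample that contributes.

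- Sensitivity 90%: n = 43 gives 20.1 points and n = 44 gives 19.8, so 44 cases. 44 / 0.75 = 58.7, rounded up to 59, as printed.
- Specificity 80%: 70 children without pathology. 70 / 0.25 = 280, as printed.

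The 59 patients therefore stand for 44 cases of either kind.

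**Step 2: apply the same method to each segment.** If both sensitivities were 90%, the need is 44 + 44 = 88 cases. That fits within 100, but only if the mix is controlled: with 100 cases, a posterior share below 44% misses the target.

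**Step 3: vary the assumed posterior sensitivity.** Entries are half the full width of the exact 95% interval, in points.

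| Posterior sensitivity | Cases needed for ±10 | 20 cases | 25 cases | 30 cases | 45 cases | 50 cases |
|---|---|---|---|---|---|---|
| 4% | 26 | 11.7 | 10.1 | 9.0 | 7.0 | 6.6 |
| 10% or 90% | 44 | 15.2 | 13.5 | 12.2 | 9.8 | 9.2 |
| 50% | 104 | 22.8 | 20.5 | 18.7 | 15.3 | 14.5 |

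Between these rows, the need is 70 cases at 20% or 80%, and 89 at 30% or 70%. As intervals: 18 of 20 gives 68.3% to 98.8%; 10 of 20 gives 27.2% to 72.8%; 45 of 50 gives 78.2% to 96.7%; 25 of 50 gives 35.5% to 64.5%.

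**Step 4: the lower enrolment figure.** At 100 participants and equal numbers of controls there are about 50 cases. An equal split leaves 25 posterior cases: a half-width of 13.5 points at 90%, and 10.1 at 4%.

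**Step 5: children or eyes.** Section 8.5 counts patients and 3.3 counts eyes. If n children have both eyes affected and the within-child correlation is ρ, the effective number of eyes is 2n / (1 + ρ). With n = 50 and an assumed ρ = 0.5, this is 100 / 1.5 = 67. Bilateral disease therefore helps, but by less than a factor of two. The plan gives neither ρ nor the share of bilateral cases.

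**The case against.** The strongest reply is that the plan does intend separate groups, as the Protocol Summary says, and that the team can control the mix: cases have known diagnoses (5.1) and are identified by the principal investigator from medical records (5.5). An even division of 100 cases gives 50 per segment, which meets ±10 points at 90%, and also at 10% or lower. If posterior sensitivity is as low as the cited studies found, 26 cases are enough, and even 0 detected out of 20 would give an exact interval of 0% to 16.8%.

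All of this stands, and it limits the point. It does not remove it, because an intention to divide the cases without a number secures neither 44 nor 26 posterior cases.

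Three stronger readings are tempting and are not supported:

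- **That the posterior group will be small.** The documents give no case mix. Section 5.2 lists five eyelid, corneal, refractive or lens conditions against about 14 vitreous, retinal, choroidal, tumour or optic nerve entries. That does not establish the mix either way, but it gives no ground for predicting an anterior-dominated sample.
- **That the dilation comparison is underpowered.** The plan gives no effect size or discordance rate for the McNemar test, so power cannot be derived from it.
- **That the conflict between 280 in 8.5 and 200 in 5.1 is the cause.** It is a separate matter. At 280 and 75% prevalence there would be 210 cases, and a posterior share of 21% would give 44 (44 / 210). That makes the gap easier to close, but still sets no number. The accrual ceiling of 200 in the Protocol Summary supports using about 100 cases here.

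**Conclusion.** The point holds in conditional form. The ±10 points in 8.5 belongs to a pooled sensitivity at 90%, and nothing in the plan secures it for posterior sensitivity, which is primary on its own. With about 100 cases, fewer than 44 posterior cases misses the target at the plan's assumed 90%, and at 20 cases the interval is about 30 points wide instead of 20. The miss is small or absent if posterior sensitivity is near 4%. It is largest at mid-range values, where even 100 posterior cases would fall just short at 50%.

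A reader might infer that the target will be missed. The documents support only that it may be. These figures assume one observation per child, 5.1's enrolment of 200 with half as controls, and the assumed range of 20 to 50 posterior cases. Counting eyes would narrow the intervals by an amount the plan does not allow one to calculate. Specificity is not at issue: 100 controls at 80% give a half-width of 8.3 points.

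**What to change.** In 5.1, state a minimum number of posterior and of anterior cases within the planned 100. At least 45 of each is one workable choice. It requires about 100 cases and cannot be met at the 100-participant lower end of the Protocol Summary range, where there are only about 50. The anterior minimum follows 3.1, which treats anterior accuracy as primary.

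In 8.5 and its copy in the Protocol Summary, replace the pooled sensitivity calculation with one per segment. Each should use its own assumed sensitivity, with the posterior value consistent with the hypothesis of poor detection, and should give the expected interval width. Say plainly that 45 cases give ±10 points only if sensitivity is about 10% or lower or about 90% or higher; at 50% the interval would be about 30 points wide. State whether the count is of children or eyes.

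The cost is a recruitment rule and a rewritten paragraph. If about 100 cases are enrolled as 5.1 plans, the total does not rise. The last posterior places may fill more slowly, and some anterior cases may have to be declined.
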